## 7. BACKGROUND AND SIGNIFICANCE

### Background and Significance

**Black women are disproportionately affected by HIV and interpersonal violence.** Black women living with HIV/AIDS (WLHA) in the US are less likely to be engaged in HIV care and adherent to antiretroviral therapy (ART) compared to other racial/ethnic groups (1-3). Black WLHA account for 61% of diagnoses among women of all races and ethnicities (4), only 56% are retained in care (1), and 49% virally suppressed (1). Black WLHA are particularly affected in San Diego County, CA, with HIV prevalence rates 8 times higher than that observed for White WLHA (5) and are underserved and understudied. Blacks on ART in San Diego are less likely to be virally suppressed than Latinos or Whites (6). Concurrently, Black women are disproportionately affected by interpersonal violence, defined as ever experiencing physical (e.g., hit, slapped, choked), sexual (e.g., forced vaginal/anal sex), and/or psychological (e.g., yelled at, belittled, controlling behaviors) abuse by a male intimate partner (e.g., spouse, boyfriend, dating partner) or non-intimate partner (e.g., relative, friend, stranger). Interpersonal violence is comprised of commonly reported forms of violence (i.e., intimate partner violence (IPV), rape, contact sexual violence, childhood abuse). Whereas the national prevalence of lifetime IPV is 45% (7), Black women report 35% higher IPV than White women (8). Moreover, although national data estimates the lifetime prevalence of rape among Black women at 21% (7), community-based samples estimate prevalence rates of rape as high as 38-54% (9-12).

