### **Medical Record Chart Abstraction**

During the passive follow-up period (7-12 months post-baseline), the research team will utilize the signed Release of Information (ROI) forms and HIPAA Authorization Forms of all study participants (participant consent collected at Baseline Study Visit), in order to request medical chart data for all participants from local HIV care providers to obtain data on clinic visits, HIV viral load, and CD4 values. Data will be entered into the REDCap Electronic Data Capturing System. These medical chart data extractions will be conducted periodically, given the staggered enrollment period.

To safeguard confidentiality, for the quantitative data collection, each participant will receive a unique patient identification number (PID) and names will never be used in conjunction with PID numbers. This unique PID number will appear on the survey, tracking forms (e.g., scrip payment receipt, cell phone tracking form), locator and screening forms. Participant confidentiality will be maintained through use of the unique PID and secure networks where data are stored. All laboratory data will be electronically transferred to the UCSD Data Management Center via password protected electronic files. At the UCSD Data Management Center, all computer files will be identifiable only by the PID number.

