#### **AIM 2**

We expect to reach our sample size utilizing partnerships established through the UCSD Center for AIDS Research (CFAR) Disparities Core Community Advisory Board (CAB), of which [name] is Director, and through standard outreach methods. Following other projects led by [name] and other members of the investigative team, we expect a retention rate of at least 85% in the first follow-up visit and another 80% in the second follow-up visit. Nevertheless, we will strive to engage and maintain our sample. To do this, we will

implement tactics to improve retention. Specifically, we will: (1) Utilize an increasing payment schedule to enhance motivation to complete study visits. Specifically, women will be offered \$30 and \$40 for completing 3- and 6-month study visits, with a \$10 bonus for completing all 3 study visits (2) collect contact information for three people (e.g., friends, family members) who would likely have knowledge of participants' whereabouts; (3) provide study cell phone number for ease of study staff calling or texting participants and participants calling or texting study staff with any questions or concerns; (4) maintain frequent contact with participants to check in about their service needs which include any linkages the study team can provide to resources in the community; and (5) as appropriate, sending text messages on participants' personal cell phone or assigned study cell phone with birthday and holiday greetings, and congratulations messages for graduations and other important events. We also will make it easy for participants to stay in touch with our team by providing a toll-free phone number, email and web addresses (in addition to the study cell phone). Given our target sample size and short follow-up period, we are confident that the aforementioned approaches will maximize retention in our study.

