## **10. HUMAN SUBJECTS**

### **Human Subjects**

**Anticipated WLHA demographics to be enrolled in LinkPositively.**

#### **AIM 1**

In Phase 1 (Aim 1), we will conduct focus groups (FGs) and in-depth interviews. Eligible participants will be Black WLHA (including transgender women) with a History of Interpersonal Violence (n=6-8 per FG; total of 4 FGs); Black WLHA (including transgender women) with a History of Interpersonal Violence who act in a professional capacity as a Peer Navigator (n=4-6; one FG). Key Informants (n=4-6) will be leadership at local clinics and community-based organizations known to provide services to women in the areas of HIV/AIDS care and domestic violence services such as UCSD Owen Clinic and Mental Health America. Phase 1 will culminate in usability testing, Beta Testing, by Black WLHA affected by interpersonal violence (n=8; 4 with histories of interpersonal violence perpetrated by a current or former intimate partner and 4 with histories of interpersonal violence perpetrated by a non-intimate partner [e.g., family member, friend, stranger]), to finalize intervention components and procedures.

## AIM 2

In Phase 2 (Aim 2), we will conduct a randomized control trial study design with follow-up. Eligible participants will self-report: (a) female gender (including transgender women), (b) Black or African American racial/ethnic background, (c) ages 18+ years, (d) HIV-positive status, (e) ever experienced physical, sexual, and/or psychological abuse by a current or former partner or non-partner (e.g., relative, friend, stranger), (f) owner of a smartphone with internet browsing capabilities, and (g) English speaking. Purposive sampling will be used to ensure that groups are balanced with respect to type of perpetrator (current or former intimate partners [e.g., spouse, boyfriend, dating, casual] and non- intimate partners [e.g., family member, friend, stranger]) and retention in HIV medical care status (linked to care but have fallen out of care [i.e., no ART prescription filled, no viral load labs, or no HIV care visits with an ART-prescribing provider in the past year] versus linked to and retained in care [i.e., ART prescription filled, viral load labs, or HIV care visits with an ART prescribing provider in the past year]). The total possible sample size for the study will be 80 women living with HIV/AIDS (WLHA). Of 80 enrolled women, 40 will be randomized to the intervention arm and 40 will be randomized to the control arm.

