## Statistical Analysis Plan

The statistical plan includes measuring feasibility of delivering the intervention, the acceptability of the LinkPositively intervention, and the impact of the intervention.

**Feasibility** The first step in assessing feasibility of delivering the intervention was by creating a Consort flow diagram tracking screening, eligibility, decision to participate, participation at baseline, and participation at 3-month and 6-month follow-ups. The second step in assessing feasibility was to compute the percentage of participants at baseline who were retained at 3-month follow-up and 6-month follow-up, and comparing proportion trends between the intervention and control groups. We used the following retention cut-off percentages to assess feasibility: a) 90+% = strong feasibility; b) 80-89% = acceptable feasibility; c) 70-79% = modest feasibility with a need for improvement; d) <70% = unacceptable.

**Acceptability** We assessed acceptability of the intervention by asking participants in the LinkPositively group about: 1) the quality rating of the program/app, 2) whether or not they received the type of program/app they were anticipating, 3) to what extent the program/app met their needs, 4) whether or not they would recommend the program/app, 5) level of satisfaction with the help received; 6) whether or not the program helped them deal more effectively with their problems, 7) level of satisfaction with the program received, and 8) whether or not they would seek help from the program/app again.

These measures of acceptability were assessed at both 3-month and 6-month follow-ups. At each timepoint, we computed mean scores and standard deviations, as well as median scores and interquartile ranges, for all continuous variables. We calculated frequency and percentages for all categorical variables.

**Intervention Impact** To estimate the preliminary effect of the intervention on primary outcomes we examined differences by group (intervention vs control) in responses to HIV care outcomes over time, ART adherence over time, and mental health outcomes over time. Responses were collected at baseline, 3-month follow-up, and 6-month follow-up. Due to the small n's, we calculated median scores and interquartile ranges for all continuous variables, and frequency/percentages for categorical variables. These statistics were stratified by group, and trends were compared, but significance could not be calculated due to low power.

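### The impact analysis compares per-visit summaries with no within-woman change and no stated set of women, so for hair and survey outcomes selective loss can look like change within an arm

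*Combined protocol and SAP*

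**What the plan says.** The impact paragraph of the Statistical Analysis Plan covers HIV care outcomes, ART adherence and mental health. On timing it says "Responses were collected at baseline, 3-month follow-up, and 6-month follow-up". On the summaries: "Due to the small n's, we calculated median scores and interquartile ranges for all continuous variables, and frequency/percentages for categorical variables". On the comparison: "These statistics were stratified by group, and trends were compared". It adds that "significance could not be calculated due to low power". It names no analysis set, denominator rule, change score, longitudinal model or missing-data method.

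The feasibility paragraph of the SAP plans a CONSORT diagram and a comparison of retention by arm. Neither is tied to the outcome analysis.

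On expected loss, protocol section 9 (Retention of Participants, Aim 2) says "we expect a retention rate of at least 85% in the first follow-up visit and another 80% in the second follow-up visit".

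The outcomes come from different sources. Under Specific Aims (Aim 2), retention in care and viral suppression are taken from medical records, and adherence from hair. Under Medical Record Chart Abstraction, the team will "request medical chart data for all participants from local HIV care providers", in months 7 to 12 after baseline. Hair and survey data are collected at the study visits. Follow-up visits may be virtual, with hair collected at home.

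**The concern.** If a woman who misses a visit is simply absent from that visit's summary, the baseline, 3-month and 6-month figures describe three different sets of women. The median or percentage can then move although no woman has changed.

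Selective loss is plausible in this trial. Recruitment deliberately mixes women who have fallen out of care with women retained in it, and poor engagement with care may go with missed study visits. The arms also differ in contact: the intervention arm has an app and a peer navigator, while control care is self-directed. Loss that differs by arm is therefore a realistic possibility. The documents do not show that it occurs.

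This is the trial's only analysis of impact, and the pilot is meant to prepare a larger trial. A reader of these tables could not tell change from attrition, although each woman's own baseline value is available.

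**Working it through.** The plan gives no sample-size, power or alpha figure, so there is none to reproduce. The check is selection arithmetic under no true change.

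**Inputs**
- Arm size (protocol section 10, Human Subjects, Aim 2): "Of 80 enrolled women, 40 will be randomized to the intervention arm and 40 will be randomized to the control arm".
- Retention r (protocol section 9): at least 0.85 at month 3. The month-6 wording is ambiguous. The natural reading is 0.80 of baseline (32 of 40). Multiplying the two gives 0.85 × 0.80 = 0.68.
- Baseline proportion: 50%, an assumption. The Background gives population figures of the same order ("only 56% are retained in care (1), and 49% virally suppressed (1"); these are not trial data.
- Who is lost: not in the documents, so a range is shown.

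**Moderate selectivity, binary outcome, 20% loss.** Let g and b be the loss probabilities in the better and worse halves. Then (g + b)/2 = 0.20 and [b/(1−b)] / [g/(1−g)] = OR. The observed proportion is 0.5(1−g)/0.80.
- OR 2: g = 0.146, b = 0.254. Observed 0.5 × 0.854/0.80 = 53.4%, a false +3.4 points.
- OR 3: g = 0.117, b = 0.283. Observed 0.5 × 0.883/0.80 = 55.2%, a false +5.2 points.

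**Extreme case, all losses from the worse half (lowest scorers for the median).** The proportion is 0.5/r. The median shift is Φ⁻¹(1 − 0.5r) SD for a normal outcome.

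| Retained | Proportion | Shift | Median shift |
|---|---|---|---|
| 85% | 58.8% | +8.8 points | +0.19 SD |
| 80% | 62.5% | +12.5 points | +0.25 SD |
| 68% (product reading only) | 73.5% | +23.5 points | +0.41 SD |

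**Other directions.** Random loss has zero expected shift. If all eight women lost from 40 come from the better half, the proportion is 12/32 = 37.5%, so the sign reverses.

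**Between arms.** Equal loss with equal selectivity gives 62.5% − 62.5% = 0. A hypothetical 10% loss in one arm and 30% in the other, a split with no source in the documents, gives:
- OR 2: 51.7% and 55.1%, a false gap of 3.4 points.
- Extreme case: 0.5/0.9 = 55.6% and 0.5/0.7 = 71.4%, a false gap of 15.9 points.

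**Same women at both visits.** In the extreme case with 32 of 40 retained, the baseline is 20/32 and month 6 is 20/32: a change of 0, against +12.5 points unpaired.

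Pairing is not a complete cure. In a simulation with an assumed baseline-to-follow-up correlation of 0.7, 80% retained and odds of loss 2 to 3 times higher per SD worse, the unpaired median shift was +0.09 to +0.12 SD. The median paired change was about −0.03 to −0.06 SD.

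**The case against.** Much can be said for the plan, and most of it stands as a limit on the point.

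- **The analysis set is not stated.** A reader might infer that the SAP restricts each summary to attenders. It does not say so. That reading comes from silence, although no rule brings absent women back in.
- **Two of the three primary outcomes are less exposed.** Chart data are requested for everyone, so a missed visit need not remove a woman from retention in care or viral suppression. What remains is that the SAP describes all impact data as responses from the three visits and does not say how chart data enter the tables. Virtual visits and home hair kits may also reduce loss of survey and hair data.
- **The larger figures can be over-read.** The 85% is a floor, so expected month-3 loss is at most 15%. The 32% loss is only one reading of the month-6 wording; the resulting 68% retention would fall in the SAP's own unacceptable band. Nothing in the documents says that the lowest scorers leave or that loss differs by arm.
- **The moderate shift is small beside sampling error.** At n = 32 and 50%, one percentage has a standard error of √(0.25/32) = 8.8 points, and a difference between arms 12.5 points. This does not remove the systematic shift, but it puts it in proportion.
- **It is a descriptive pilot.** The SAP calls the effect preliminary and claims no significance. Low power concerns precision, however. It is no reason to prefer an unpaired summary, because a paired one needs no test.
- **Differential loss would be visible** in the planned retention comparison. That shows how many women left each arm, but not whether they were doing worse at baseline.

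**Conclusion.** The point holds for hair-measured adherence and for survey outcomes, including mental health. The SAP reads change from per-arm, per-visit summaries without within-woman change and without naming the women in each. Given the expected loss, those summaries will probably rest on different women.

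At 20% loss, with no true change and a 50% baseline, a plausible false within-arm gain is about 3 to 5 points. The upper bound is 12.5 points, or 0.25 SD in a median. These sizes illustrate assumed loss patterns and are not estimates for this trial.

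A reader might go further and infer that the between-arm comparison is biased, or that all primary outcomes are affected. The documents support neither. Similar loss in both arms largely cancels, and the chart outcomes do not depend on attendance. This should be fixed, but no confirmatory claim rests on it.

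**What to change.** 1. For hair and survey outcomes, report by arm each woman's change from her own baseline at 3 and 6 months, with n. For binary outcomes, count women who gained, kept, lost or never had the outcome. Show any per-visit summaries on the same women.
2. Beside the retention comparison already planned, tabulate baseline outcome values by arm for women who attended and women who missed each follow-up visit.
3. For retention in care and viral suppression, state that all randomised women with chart data are analysed as randomised, whether or not they attended study visits.

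A baseline-adjusted repeated-measures model is optional; the descriptive approach can stay.

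No new data are needed. The cost is SAP wording, a few more tables and, since the SAP is written in the past tense, probably some re-tabulation. The paired summaries will have smaller n. Pairing removes most of the artefact but not every missing-data bias, which is why the table in item 2 is needed.

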##### **Aim 2: Conduct a pilot randomized controlled trial to assess the feasibility, acceptability and preliminary impact of the *LinkPositively* intervention for Black WLHA affected by interpersonal violence, in preparation for a large-scale R01.**

Eighty Black WLHA ever experiencing interpersonal violence will be randomly assigned (1:1) to receive *LinkPositively* or standard of care Ryan White services, with self-reported, biological, and clinical outcomes collected at baseline, 3- and 6-month follow-up visits. Intervention use data will be collected throughout the intervention period to examine feasibility, acceptability, and the associations between components used and study outcomes. Primary outcomes are retention in HIV care, ART adherence, and viral suppression, whereas socio-structural mechanism of change variables are social support and

activation of social support networks, self-efficacy, and utilization of ancillary support services. To minimize recall bias and/or social desirability bias, that may occur with the use of audio computer-assisted self-interviews, we will use objective data to measure the main outcomes. Retention in HIV care and viral suppression will be based on medical record data and ART adherence will be measured using hair samples assayed for tenofovir and emtricitabine. The proposed study will benefit the advancement of HIV prevention science by harnessing mobile technology to promote retention in HIV care and ART adherence among US Black WLHA affected by interpersonal violence and co-occurring adverse mental health and substance abuse – an underserved, marginalized population. If the LinkPositively intervention is efficacious through an eventual R01 mechanism, it will change the paradigm for addressing the unique HIV treatment needs for Black women dually affected by HIV and interpersonal violence.

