contacted for follow-up assessments. Informed consent, completion enrollment paperwork, and assessments will occur in field offices in San Diego County (UC San Diego AntiViral Research Center, located at [name]), Los Angeles County (Charles R. Drew University of Medicine and Science, Clinical and Translational Science Institute, [name]), Alameda County (WORLD, located at [name]), Oklahoma City (Guiding Right Offices, [name], [name], and [name]) and Tulsa County (Guiding Right, Inc., [name]). Following the baseline visit, participants will be randomized using a randomization sequence at a 1:1 ratio into the intervention or control arm on a rolling basis.

**All Study Visits.** At all study visits (Baseline, Follow-Up 1, Follow-Up 2), participants will undergo an interviewer-administered quantitative survey and biological sample collection (hair). An increasing payment schedule will be used to enhance motivation to complete surveys. Specifically, women will receive \$25 for completing the baseline visit, \$30 for completing the 3-month follow-up visit, and \$40 for completing the 6-month follow-up visit, with a \$10 bonus for completing all 3 visits. Due to the ongoing COVID-19 pandemic, follow-up study visits may occur virtually, over the secure video conference platform Zoom. For all in-person study activities, participants and staff will be required to wear face masks and physically distance when feasible. If participants do not have access to a face mask, one will be provided to them upon entry to the private research office space. Additionally, all participants will be screened for symptoms of COVID-19 by the Research Associate one day in advance of all in-person study visits, and again upon arrival at the private research office space.

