**Biological Sample Collection.** After completion of the interviewer-administered survey at baseline, 3- and 6-month follow-up, the Project Coordinator or Research Associate (trained in hair sample collection by [name]) will retrieve a hair sample from participants. All participants will be compensated \$25 per visit, upon completion of hair sample collection. The hair sample collection kit is comprised of scissors, piece of tin foil, two patient labels, plastic (e.g., Ziploc) bag, alcohol swabs, and desiccant pellet. The following steps will be followed for hair sample collection: (1) Clean the blades of a pair of scissors with an alcohol pad; (2) Lift up the top layer of hair from the occipital region of the scalp at the back of the participant's head. Isolate a small thatch of hair (~100 fibers of hair) from underneath this top layer; (3) Cut the small hair sample as close to the scalp as possible. For short or cropped hair, the Project Coordinator can let hair fall directly into the piece of tin foil. For braided hair, cut hair thatch from in-between braids or dread locks; (4) Keep fingers on the part of the hair that was furthest away from the scalp and put the hair sample down on an unfolded piece of tin foil; (5) Put a thin label over the end of the hair sample that was furthest away from the scalp; (6) Refold the foil over to completely enclose the hair and place a study ID label on the folded piece of foil; (7) Place the folded piece of foil inside the plastic bag and seal the bag. Hair samples will then be securely mailed to the UCSF Hair Analytical Laboratory, led by [name], where liquid chromatography/tandem mass spectrometry will be used to assess antiretroviral concentrations in hair samples over the past 3 months (3cm of hair). Given the ongoing COVID-19 epidemic, all participants will also be trained in hair self-collection at their first (baseline) visit, and given labeled kits for self-collection of hair samples at home should the participant's follow-up visit occur virtually. If the follow-up visits occur virtually, study staff will arrange a date and time to pick up the hair samples at a location convenient and safe for the participant, shortly after the virtual study visit.

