### **24. BIOLOGICAL MATERIALS TRANSFER AGREEMENT**

We plan to collect hair samples from participants at all study visits. The following steps will be followed for hair sample collection: (1) Clean the blades of a pair of scissors with an alcohol pad; (2) Lift up the top layer of hair from the occipital region of the scalp. Isolate a small thatch of hair (~100 fibers of hair) from underneath this top layer; (3) Cut the small hair sample as close to the scalp as possible. For short or cropped hair, the Project Coordinator can let hair fall directly into the piece of tin foil. For braided hair, cut hair thatch from in-between braids or dread locks; (4) Keep fingers on the part of the hair that was furthest away from the scalp and put the hair sample down on an unfolded piece of tin foil; (5) Put a thin label over the end of the hair sample that was furthest away from the scalp; (6) Refold the foil over to completely enclose the hair and place a study ID label on the folded piece of foil; (7) Place the folded piece of foil inside the plastic bag and seal the bag.

The hair samples will then be securely mailed to the UCSF Hair Analytical Laboratory, led by [name], where liquid chromatography/tandem mass spectrometry will be used to assess antiretroviral concentrations in hair samples over the past 3 months (3cm of hair).

Given the above plan, a biological materials transfer agreement (MTA) will be secured prior to any biological sample transfer between UC San Diego and UC San Francisco.

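### Continuous outcomes with a planned baseline value are compared only as unadjusted per-arm summaries; a baseline-adjusted arm difference with a 95% CI would use the planned data better

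*Combined protocol and SAP*

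**What the plan says.** Section 6 (Specific Aims, Aim 2) plans "self-reported, biological, and clinical outcomes collected at baseline, 3- and 6-month follow-up visits". Section 9 repeats this for the survey and the hair sample under All Study Visits. Under Biological Sample Collection, hair is taken "After completion of the interviewer-administered survey at baseline, 3- and 6-month follow-up". Section 24 agrees: "We plan to collect hair samples from participants at all study visits". Section 20 pays for hair at all three visits. Section 14 (Physical Risks) differs, naming hair collection at the 3- and 6-month assessments only.

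Hair, assayed for tenofovir and emtricitabine, serves the ART adherence outcome. The other two primary outcomes, retention in care and viral suppression, come from medical records (section 6). Section 9 (Medical Record Chart Abstraction) has those records requested 7 to 12 months after baseline and states no baseline window.

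The SAP's Intervention Impact paragraph covers HIV care, ART adherence and mental health outcomes at the three time points. It gives medians and interquartile ranges for continuous variables, and frequencies and percentages for categorical ones. It ends: "These statistics were stratified by group, and trends were compared, but significance could not be calculated due to low power". It names no model, covariate, between-arm estimate or confidence interval.

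**The concern.** The plan gives low power as its reason for stopping at description. Yet it leaves unused a source of precision that needs no extra women or visits: each woman's own starting value on the outcome.

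In the SAP's display, baseline is only the first point of each arm's series. A reader who sets the two series side by side is in effect comparing either the follow-up values or the changes from baseline. The first carries any chance baseline difference straight into the comparison. The second over-corrects for it when the correlation is below 1, so regression to the mean can pass for a trend.

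Chance differences are plausible. The sample deliberately mixes women who have fallen out of care with women retained in it (section 9, Study Population, Aim 2), and no stratified randomisation is described. The stake is the quality of the preliminary effect estimate that is meant to prepare a larger trial.

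**Working it through.** **Inputs from the documents**
- Arm sizes (section 10): "Of 80 enrolled women, 40 will be randomized to the intervention arm and 40 will be randomized to the control arm".
- Retention (section 9, Retention of Participants): "we expect a retention rate of at least 85% in the first follow-up visit and another 80% in the second follow-up visit". If 80% of all randomised women remain at month 6, that is 0.80 × 40 = 32 per arm. If the two rates multiply, 0.85 × 0.80 = 0.68, or about 27 per arm.
- Alpha, power, effect size, SD and baseline-to-follow-up correlation (rho): none is stated, so there is no planned figure to reproduce.

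**Assumptions**
- SD of 1 at every visit; rho of 0.3, 0.5 or 0.7.
- For the power illustration only: two-sided alpha of 0.05 and a true difference of 0.5 SD.

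**Variance of the arm difference, relative to follow-up only**
- Follow-up value only: 1
- Change from baseline: 2(1 − rho)
- Baseline-adjusted (ANCOVA): 1 − rho², in large samples
- Adjusted relative to change: (1 − rho²) / [2(1 − rho)] = (1 + rho)/2

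| rho | Change | Adjusted | Cut vs follow-up only | Cut vs change |
|---|---|---|---|---|
| 0.3 | 1.40 | 0.91 | 9% | 35% |
| 0.5 | 1.00 | 0.75 | 25% | 25% |
| 0.7 | 0.60 | 0.51 | 49% | 15% |

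**Interval width**
- At 32 per arm, the follow-up-only SE is √(2/32) = 0.250 SD, so the 95% half-width is 1.96 × 0.250 = 0.49 SD. Multiplying by √(1 − rho²) gives 0.47, 0.42 and 0.35 SD at rho 0.3, 0.5 and 0.7.
- At 27 per arm, 0.53 SD becomes 0.51, 0.46 and 0.38 SD.

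**Small-sample cost.** Estimating the slope multiplies the adjusted variance by (N − 3)/(N − 4). With N = 64 this is 61/60 = 1.017, so at rho = 0 adjustment is about 1.7% worse than follow-up only. Break-even is rho = 1/√(N − 3): 1/√61 = 0.13 at 32 per arm and 1/√51 = 0.14 at 27 per arm.

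**Simulation check** (20,000 runs, 32 per arm). SEs for follow-up only / change / adjusted:
- rho 0.3: 0.251 / 0.298 / 0.242
- rho 0.5: 0.250 / 0.249 / 0.217
- rho 0.7: 0.250 / 0.194 / 0.180

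For the same normal data, a difference in medians had an SE of about 0.31.

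**Power illustration** (two-sample t-test, 32 per arm, 0.5 SD). Follow-up only gives 50% throughout. At rho 0.3, 0.5 and 0.7, change gives 38%, 50% and 72%, and adjusted gives 54%, 62% and 79%.

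**The case against.** The strongest reply is that there is no contrast here to sharpen. The SAP gives no arm difference and no interval, and it runs no test. That gap is more basic, and once it is filled, baseline adjustment is one detail of the specification. This stands as a matter of order. It does not remove the point: a raw difference with an interval would still be less precise for any moderate rho, and both can be settled in one edit.

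Four stronger readings are tempting, and the documents do not support them.

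- **Baseline values exist for every woman.** Collection is a plan, nothing shows that it was complete, and section 14 omits baseline hair.
- **Adjustment is free and never worse.** That holds only in large samples, as the break-even figures show. Rho could be low for hair: only two drugs are assayed, and women with no ART prescription filled in the past year may be enrolled, so many baseline values may sit at the floor.
- **Power rises from 50% to 79%.** That is against follow-up only, at rho 0.7. Against change it goes from 72% to 79%. The SAP runs no test and summarises by medians, so mean-based power is only a gloss.
- **All three primary outcomes gain.** The rho formulas are for continuous outcomes. Retention and suppression come from charts with no stated baseline window.

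The SAP is also written in the past tense, so a model added now may follow sight of the data.

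**Conclusion.** The point holds for continuous outcomes with a planned baseline value: the survey scores, and the hair level once the passages on baseline hair are reconciled. For these, the plan forgoes a better estimator on data it already intends to collect.

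The size of the gain rests on an assumed rho and equal SDs at baseline and follow-up. It is substantial at rho 0.5, where the interval is 13% narrower (1 − √0.75) than under either unadjusted contrast. It is modest against follow-up only at rho 0.3, and small or nil below about 0.13. No gain is established for the binary, record-based outcomes.

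This is an inexpensive improvement. The pilot can still be interpreted without it, but its effect estimates would probably be noisier than they need be.

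**What to change.** In the SAP's Intervention Impact paragraph:

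1. For each continuous outcome with a planned baseline value, report the between-arm difference at 3 and 6 months from a model with arm, visit, arm-by-visit and the outcome's baseline value, with a 95% CI. Use survey scores as collected. Use hair level on a log scale, or rank-transformed if many values are undetectable.
2. For binary record-based outcomes, give a baseline-adjusted risk difference (standardised from a logistic model) only where a baseline status can be abstracted from the charts. Otherwise give the unadjusted difference.
3. Label these estimates preliminary, and post hoc if the model was added after the data were seen. Keep the descriptive tables.
4. State a simple rule for missing baseline values, such as a missing-baseline indicator.
5. Reconcile section 14 with sections 9, 20 and 24 on baseline hair.

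The cost is SAP wording and a short model run. Statistically, it spends one degree of freedom and requires a choice of scale and the missing-baseline rule. It needs no additional women, visits or samples beyond those planned.
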